6.2.1 Baseline Descriptive Statistics

The following patient data will be recorded: age, gender, height, weight, date of admission, date of discharge, laterality, surgical approach, implants used, duration of surgery, contamination, ASA, comorbidities (smoking, cardiac history, diabetes etc.), CBC (WBC, PCV, HGB, RBC, indices, platelet count, differential), and medications. All of this information will be accessible in the patient's medical record.

6.3 Sample Size

184 subjects will be enrolled

6.4 Enrollment/Randomization/Masking Procedures

We will utilize randomization.com to generate a randomization assignment for all 184 participants. Someone that is not a stakeholder in the study will make randomization envelopes, which include the study ID number, the treatment assignment, and dosage specifics. These randomization envelopes will then be distributed to the anesthesiologist pre-operatively by the authorized researcher after informed consent is obtained.

6.5 Breaking the Study Blind/Participant Code

If there is any adverse event related to the drug, we will break the blind for the subject and randomization will be disclosed to the patient.

7 Assessment of Safety

An **adverse event** (AE) is any symptom, sign, illness or experience that develops or worsens in severity during the course of the study. Intercurrent illnesses or injuries should be regarded as adverse events. Abnormal results of diagnostic procedures are considered to be adverse events if the abnormality:

- results in study withdrawal

CONFIDENTIAL

This material is the property of the NYU School of Medicine and Langone Medical Center. Do not disclose or use except as authorized in writing by the study sponsor

- is associated with a serious adverse event
- is associated with clinical signs or symptoms
- leads to additional treatment or to further diagnostic tests
- is considered by the investigator to be of clinical significance

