3.1 Description of Study Design

PRE-SCREENING PHASE/CONSENTING PHASE:

Surgeons will inform eligible patients of the study during their pre-surgical visit in their office. The surgeons will use an IRB-approved recruitment flyer to help explain the study to the eligible patient. If the patient is agreeable, a member of the research team will provide further details and ask the patient to participate on day of surgery. Informed consent will be obtained on DOS when the patient is in the pre-operative holding room by an authorized research member.

BASELINE ASSESSMENTS:

After informed consent has been obtained, participants will complete a total of 3 PROMIS assessments (Upper Extremities, Pain Intensity and Global Physical Health) before undergoing their TSA surgery.

RANDOMIZATION PHASE:

Subjects scheduled to undergo TSA will be randomized to either the Bupivacaine 0.5% plus Liposomal bupivacaine Or Bupivacaine 0.5% group. Randomization of each subject will be done on day of surgery using randomization.com software to generate the assignment.

TREATMENT PHASE:

Subjects in the Bupivacaine plus Liposomal bupivacaine group will receive an interscalene nerve block with 10mL 0.5% Bupivacaine and 10mL of Liposomal bupivacaine. The control group will receive an interscalene nerve block with 20mL 0.5% Bupivacaine HCL. The anesthesiologist will NOT be blinded to what solution is being injected, as liposomal bupivacaine is a white fluid while bupivacaine is clear. All other stakeholders (patient, surgeon, other caregivers, and research staff collecting the data) will be blinded to the patient’s group assignment.

POST-OPERATIVE PHASE:

After initial recruitment, subjects’ pain will be assessed via visual analog scale (VAS) by nursing staff during the post-operative period as per standard of care. The VAS pain scores are collected and documented in the patient’s electronic medical record. Additionally, a standardized regimen of pain medication will be given to all subjects who are enrolled. The pain medications given to patients are standard of care medications and vary based on pain level. The clinical staff determines this for each patient.

CONFIDENTIAL

This material is the property of the NYU School of Medicine and Langone Medical Center. Do not disclose or use except as authorized in writing by the study sponsor

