5.1 Potential Risks

Bupivacaine used for this study is the standard of care for ISB. Liposomal Bupivacaine (EXPAREL®), a second study drug, has recently been approved by the FDA for use in interscalene blocks.

The potential risks associated with bupivacaine include neurologic and cardiac toxicity, if injected intravascularly. However, the risk is very low because a trained anesthesiologist using ultrasound guidance will perform the nerve block. This allows the anesthesiologist to see and avoid blood vessels when administering the medication. Additionally, the syringe of the local anesthetic will be aspirated prior to injection to ensure that the block needle tip is not intravascular.

The use of Liposomal Bupivacaine or Exparel® in this study is experimental and may cause side effects. Exparel® has recently been approved by the FDA to be used in interscalene blocks. The potential risks associated with Exparel® include nausea, constipation, and fever. In addition, there can be temporary sensory and motor loss, depending on the dosage, site of injection and duration of the nerve block. However, the amount (10mL) used in this study meets FDA dosage-regulations for this medication.

Potential Benefits

Study subjects may experience better pain control, improved satisfaction, decreased need for opioids and reduced incidence of side effects. If the study is not inconclusive, the study's results may benefit future patients by showcasing that Liposomal Bupivacaine improves pain control beyond 24hours in an ISB. Additionally, advocate for the use of Liposomal Bupivacaine as the standard of care for peri- and postoperative pain control in future patients undergoing TSA.

6 Statistical Analysis

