6.2 Analysis of Endpoints

Primary Endpoints:

Opioid utilization (expressed as oral morphine mg equivalents) used during initial 24-72 hours post-operative period after surgery.

Secondary Endpoints:

CONFIDENTIAL

This material is the property of the NYU School of Medicine and Langone Medical Center. Do not disclose or use except as authorized in writing by the study sponsor

Duration of opioid use
Patient reported pain scores (VAS)
Length of stay
Progress with physical therapy
Reported long-term narcotic use at home
Discharge location: home, acute rehab or skilled nursing facility
Documented opioid refills
Adverse events such as respiratory depression, hypoventilation, reintubation, nausea, constipation

The analysis of opioid use, VAS, and PROMIS assessments will rely on a univariate analysis of variance model for mean score. This model is in the class of models commonly known as unirep-ANOVA models. It assumes that the mean score is a function of elapsed time and the treatment regimen assigned. This model considers the fact that the subject's repeated measures are correlated. The fitted model will provide statistical estimates of the mean levels, the treatment-effect differences between mean levels, the standard deviation, the intra-class correlation coefficient, 95% CIs, standard errors (SE), and statistical hypothesis tests. The estimates of means will be used to compute summary criteria such as area under the curve (AUC) for each regimen. All estimates reported will be presented their 95% CIs.

All endpoints will be evaluated as fits the data set with graphical figures such as scatter plots, box-and-whisker plots, and frequency histograms to visualize the distribution of these outcomes and their relationships to covariates and treatment assignment. When appropriate descriptive graphical and tabular methods will also be estimated and presented in a graphical figure.

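### Section 6.5 tells the patient their allocation after any adverse event judged drug-related, without limit by seriousness, clinical need or timing, so some patients can be unblinded while their outcomes are still being collected

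*Combined protocol and SAP*

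**What the plan says.** Section 6.5 is a single sentence. Its trigger and action are "If there is any adverse event related to the drug, we will break the blind for the subject", and the person told is the patient: "we will break the blind for the subject and randomization will be disclosed to the patient". It does not mention seriousness, severity, clinical need, the treating clinician or the time of disclosure.

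Other sections bear on it:

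- The opening of section 7 defines an adverse event broadly, as "any symptom, sign, illness or experience that develops or worsens in severity during the course of the study".
- Section 5.1 states: "The potential risks associated with Exparel® include nausea, constipation, and fever".
- Section 6.2 lists among the secondary endpoints "Adverse events such as respiratory depression, hypoventilation, reintubation, nausea, constipation".
- Section 3.1 leaves only the anesthesiologist unblinded: "All other stakeholders (patient, surgeon, other caregivers, and research staff collecting the data) will be blinded".
- Section 6.1 bases its intention-to-treat rationale on a patient who does not know the assignment.
- Section 7.2.2 has a clinician grade every event in five causality categories. Section 6.5 does not say which of these count as related, or whether the drug means liposomal bupivacaine alone or either study drug.

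On data sources, section 3.1 has research staff visit inpatients between 24 and 72 hours to obtain and verify pain medication. Patients discharged earlier keep a diary and are telephoned. Pain, opioid use and function are followed up on POD 7, 14 and 30. The diary in 14.3 asks for side effects, with nausea as an example, beside pill counts and pain scores.

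**The concern.** The rule is wide enough for a mild, expected symptom to lead to disclosure, provided a clinician judges it related. The same symptoms are endpoints, and the diary that collects opioid use and pain also collects them. One telephone call could therefore both gather the outcome and reveal the trigger.

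A patient who learns that they did, or did not, receive the long-acting product may take opioids differently or rate pain differently from then on. They may also tell the blinded caller. The trigger arises after randomisation and could differ between arms. Section 2.1 (Statistical Hypotheses) also attributes nausea and constipation to opioids, so the chance of being unblinded may depend on the primary outcome itself. At stake is the blinded comparison of opioid use and pain in whatever share of patients is affected.

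**Working it through.** **Text check.** Three questions decide whether the gap is real.

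1. *Does anything narrow the trigger?* Sections 7.1 and 7.2.1 define seriousness and severity, but 6.5 uses neither. No other section restricts the rule, delays disclosure or plans an analysis of unblinded patients.
2. *Can an expected, mild event meet it?* Yes, if judged related. Nausea fits the adverse event definition, is a named risk in 5.1 and is an endpoint in 6.2. Section 7.2.2 decides relatedness.
3. *Can disclosure fall before outcomes are complete?* Yes. The primary window in 6.2 is 24 to 72 hours and follow-up runs to POD 30, while 6.5 sets no time.

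**Size.** The plan gives no unblinding rate, no effect of disclosure, no SD and no alpha, so there is no figure to reproduce. What follows is an illustration.

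Input from the documents: 146 evaluable (4.6), so 146/2 = 73 per arm if the loss is equal.

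Assumptions: a true null; a simple two-sided 5% normal comparison of two means; a fraction p of each arm unblinded; reported use shifted by s SD in an unblinded patient.

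- SE of the difference = sqrt(2/73) = 0.166 SD.
- Bias, both arms shifting in opposite directions, all told in time = 2 × p × s.
- Bias, if only one arm shifts or only half the disclosures come in time = p × s.
- Bias, if both limits apply = p × s / 2.
- Rejection probability = Φ(bias/SE − 1.96) + Φ(−bias/SE − 1.96).

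With p = 0.20 and s = 0.3:

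| Scenario | Bias (SD) | Rejection under the null |
|---|---|---|
| Opposite shifts in both arms, all in time | 2 × 0.20 × 0.3 = 0.12 | 11.2% |
| One arm shifts, or half come too late | 0.20 × 0.3 = 0.06 | 6.5% |
| Both limits apply | 0.20 × 0.3 / 2 = 0.03 | 5.4% |

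At p = 0.20, about 184 × 0.20 = 37 enrolled patients would be told.

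**Sensitivity, opposite shifts in both arms, all in time.** With p = 0.05 and s from 0.2 to 0.5, rejection is 5.2% to 6.1%. With p from 0.10 to 0.30 over the same s, it runs from 5.7% (bias 0.04 SD) to 44% (bias 0.30 SD). If only one arm shifts, the upper corner falls to a bias of 0.30 × 0.5 = 0.15 SD and 14.8%.

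**The case against.** Four points can fairly be made for the plan.

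*Unblinding for safety is proper care, and a code-break section is an exception to masking.* This stands. A reader might infer that 6.5 flatly contradicts 3.1, but it does not. The weakness is that the exception is wider than a safety purpose needs and works against the intent of 3.1 and 6.1.

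*The event must be judged related.* This also stands. Since the protocol attributes nausea and constipation to opioids too, many cases may be graded unlikely or not related. A reader might infer that nausea will unblind patients routinely. The documents give no event rates, so that cannot be said. However, 6.5 does not exclude the possibly related grade.

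*The primary outcome is not purely self-reported.* This stands in part. Inpatient opioid use is verified by staff, and the diary and call apply only after discharge before 72 hours. Length of stay is not given, so the self-reported share is unknown. Pain scores remain the patient's own rating in either setting, and an inpatient told early could still change how much opioid they use.

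*Late disclosure cannot affect opioid use already taken.* This stands for the primary outcome. It does not protect the POD 7, 14 and 30 reports.

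**Conclusion.** The gap in wording is certain; its effect on the result is not. As written, 6.5 removes patient blinding for those whose event is judged drug-related, and only for opioid use, pain scores and function arising or reported after disclosure. Post-discharge diary and telephone data are most exposed.

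A reader might infer that self-reported outcomes are unblinded across the trial. The documents do not support that: patients without a related event, and all data from before disclosure, are untouched.

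The bias cannot be sized from the documents. In the middle illustration the false-positive rate is between about 5.4% and 11%, depending on whether one or both arms shift and how many disclosures come in time. A reader might take the 44% corner as the expected harm. It needs 30% unblinded in each arm, half-SD shifts in opposite directions and every disclosure in time, and nothing in the documents supports that combination. The point is a cheap improvement worth making, not evidence that the primary comparison is invalid.

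**What to change.** Reconcile 6.5 with 3.1 and 6.1 in a reworded paragraph:

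- Remove automatic disclosure to the patient for non-serious events where no management decision depends on the allocation, and defer it until that patient's POD 30 data are complete.
- Keep unblinding available whenever the treating clinician judges it necessary, and for serious events.
- Keep the staff who collect outcomes blinded in all cases.
- State which relatedness categories count and which drug is meant.
- Log the date, time and reason of each unblinding.
- Add a sensitivity analysis of the primary outcome and pain scores that addresses data collected after unblinding. Keeping these patients in the main analysis already follows from the intention-to-treat principle in 6.1.

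The cost is one amended paragraph, a short log entry per case and one additional analysis. The downside is that patients with non-serious events learn their allocation later.

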7.1 Definition of Serious Adverse Events (SAE)

Serious Adverse Event

Adverse events are classified as serious or non-serious. A **serious adverse event** is any AE that is:

- fatal
- life-threatening
- requires or prolongs hospital stay
- results in persistent or significant disability or incapacity
- a congenital anomaly or birth defect
- an important medical event

Important medical events are those that may not be immediately life threatening, but are clearly of major clinical significance. They may jeopardize the subject, and may require intervention to prevent one of the other serious outcomes noted above. For example, drug overdose or abuse, a seizure that did not result in in-patient hospitalization or intensive treatment of bronchospasm in an emergency department would typically be considered serious.

All adverse events that do not meet any of the criteria for serious will be regarded as **non-serious adverse events**.

7.2 Classification of an Adverse Event

7.2.1 Severity of Event

For AEs not included in the protocol defined grading system, the following guidelines will be used to describe severity.

1. **Mild** – Events require minimal or no treatment and do not interfere with the participant’s daily activities.
2. **Moderate** – Events result in a low level of inconvenience or concern with the therapeutic measures. Moderate events may cause some interference with functioning.
3. **Severe** – Events interrupt a participant’s usual daily activity and may require systemic drug therapy or other treatment. Severe events are usually potentially life-threatening or incapacitating.

7.2.2 Relationship to Study Agent

The clinician’s assessment of an AE’s relationship to study agent (drug, biologic, device) is part of the documentation process, but it is not a factor in determining what is or is not reported in the study. If there is any doubt as to whether a clinical observation is an AE, the event will be reported. All AEs must have their relationship to study agent assessed. For all collected AEs, the clinician who examines and evaluates the participant will determine the AE’s causality based on temporal relationship and his/her clinical judgment. The degree of certainty about causality will be graded using the categories below.

1. **Definitely Related** – There is clear evidence to suggest a causal relationship, and other possible contributing factors can be ruled out. The clinical event, including an abnormal laboratory test result, occurs in a plausible time relationship to drug administration and cannot be explained by concurrent disease or other drugs or chemicals.
2. **Probably Related** – There is evidence to suggest a causal relationship, and the influence of other factors is unlikely. The clinical event, including an abnormal laboratory test result, occurs within a reasonable

CONFIDENTIAL

This material is the property of the NYU School of Medicine and Langone Medical Center. Do not disclose or use except as authorized in writing by the study sponsor

- time after administration of the drug, is unlikely to be attributed to concurrent disease or other drugs or chemicals, and follows a clinically reasonable response on withdrawal).
3. **Possibly Related** – There is some evidence to suggest a causal relationship (e.g., the event occurred within a reasonable time after administration of the trial medication). However, other factors may have contributed to the event (e.g., the participant’s clinical condition, other concomitant events). Although an AE may rate only as “possibly related” soon after discovery, it can be flagged as requiring more information and later be upgraded to “probably related” or “definitely related,” as appropriate.
 4. **Unlikely to be related** – A clinical event, including an abnormal laboratory test result, whose temporal relationship to drug administration makes a causal relationship improbable (e.g., the event did not occur within a reasonable time after administration of the trial medication) and in which other drugs or chemicals or underlying disease provides plausible explanations (e.g., the participant’s clinical condition, other concomitant treatments).
 5. **Not Related** – The AE is completely independent of study drug administration, and/or evidence exists that the event is definitely related to another etiology. There must be an alternative, definitive etiology documented by the clinician.

[name] will be responsible for determining whether an AE is expected or unexpected. An AE will be considered unexpected if the nature, severity, or frequency of the event is not consistent with the risk information previously described for the study agent.

7.3 Time Period and Frequency for Event Assessment and Follow-Up

The occurrence of an AE or SAE may come to the attention of study personnel during study visits and interviews of a study participant presenting for medical care, or upon review by a study monitor. All AEs including local and systemic reactions not meeting the criteria for SAEs will be captured on the appropriate RF. Information to be collected includes event description, time of onset, clinician’s assessment of severity, relationship to study product (assessed only by those with the training and authority to make a diagnosis), and time of resolution/stabilization of the event. All AEs occurring while on study must be documented appropriately regardless of relationship. All AEs will be followed to adequate resolution.

Any medical condition that is present at the time that the participant is screened will be considered as baseline and not reported as an AE. However, if the study participant’s condition deteriorates at any time during the study, it will be recorded as an AE. UPs will be recorded in the data collection system throughout the study.

Changes in the severity of an AE will be documented to allow an assessment of the duration of the event at each level of severity to be performed. AEs characterized as intermittent require documentation of onset and duration of each episode.

The PI will record all reportable events with start dates occurring any time after informed consent is obtained until 7 (for non-serious AEs) or 30 days (for SAEs) after the last day of study participation. At each study visit, the investigator will inquire about the occurrence of AE/SAEs since the last visit. Events will be followed for outcome information until resolution or stabilization.

All unresolved adverse events will be followed by the investigator until the events are resolved, the subject is lost to follow-up, or the adverse event is otherwise explained. At the last scheduled visit, the investigator will instruct each subject to report any subsequent event(s) that the subject, or the subject’s personal physician, believes might reasonably be related to participation in this study. The investigator will notify the study sponsor of any death or adverse event occurring at any time after a subject has discontinued or terminated study participation that may reasonably be related to this study. The sponsor will also be notified if the investigator should become aware of the development of cancer or of a congenital anomaly in a subsequently conceived offspring of a subject that has participated in this study.

CONFIDENTIAL

This material is the property of the NYU School of Medicine and Langone Medical Center. Do not disclose or use except as authorized in writing by the study sponsor

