Duration of IP administration	Once during surgery
Population	184 participants scheduled for total shoulder arthroplasty (TSA)
Study Sites	NYU Langone Orthopedic Hospital
Number of participants	184
Description of Study Agent/Procedure	Injection of 20mL 0.5% Bupivacaine HCL versus 10mL Liposomal Bupivacaine plus 10mL Bupivacaine 0.5% in an Interscalene block for TSA
Reference Therapy	Reference is Bupivacaine 0.5% for Interscalene block
Key Procedures	Interscalene nerve block with Liposomal Bupivacaine + Bupivacaine 0.5%
Statistical Analysis	Intention-to-treat analysis will be performed with mean, t-tests, within and between group ANOVA and linear regression,

CONFIDENTIAL

This material is the property of the NYU School of Medicine and Langone Medical Center. Do not disclose or use except as authorized in writing by the study sponsor

1 Key Roles

Principal Investigator:

[name]

Assistant Professor of Anesthesiology
Department of Anesthesiology, Perioperative care and Pain Medicine
NYU Langone Orthopedic Hospital
NYU Langone Health
[name]
[name]
[contact]

Co-Investigators:

[name]

Professor of Anesthesiology
Department of Anesthesiology, Perioperative care and Pain Medicine
NYU Langone Orthopedic Hospital
NYU Langone Health
[name]
[name]

[name]

Assistant Professor of Orthopedic Surgery
Department of Orthopedic Surgery
NYU Langone Orthopedic Hospital
NYU Langone Health
[name]
[name]

2 Background and Specific Aims

With the growing elderly population, the number of total shoulder arthroplasty (TSA) surgeries is increasing. Nationwide, the total and partial shoulder replacements increased from about 18,000 in 2000 to over 45,000 in 2013 according to the American Academy of Orthopedic surgeons (AAOS). One of the greatest drivers of cost following TSA has been shown to be discharge disposition. Effective pain control after surgery is paramount because it facilitates rehabilitation and decreases hospital length of stay. Additionally, it may increase the likelihood of patients being discharged to their home rather than a rehabilitation or skilled nursing facility.

TSA is a procedure that is well confined within the dermatomal distribution of an interscalene brachial plexus nerve block (ISB), making it an ideal procedure to both evaluate and compare the regional potential of varying agents. Although the analgesic coverage is typically ideal, single shot injection of the long acting

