Occupational and physical therapy progress and activity goals will be reviewed. As per standard of care, motor testing of the operated shoulder and arm will be assessed during these visits. This includes: No weight bearing exercises will be performed as per surgeon's instructions and the nursing staff will continue to obtain VAS pain scores.

[figure not shown]
During the 24-72 hour post-operative period, research staff will visit the patient while they are in the hospital to obtain and verify the pain medication taken. If the patient is discharged before the 72-hour period, the research staff will give the patient a copy of a medication record diary to complete. Additionally, the staff member will call the patient within 1-2 business days to obtain the remaining opioid utilization information.

After discharge, the research staff will continue to follow up with the patient on POD 7, POD 14 and POD 30 to assess pain scores, opioid usage patterns, and functional status. The pain intensity PROMIS assessment will be administered during each phone call. Additionally, on POD 30, participants will complete the Upper Extremity PROMIS form. Research staff will verify documented opioid refills through Epic and pharmacy records.

CONFIDENTIAL

This material is the property of the NYU School of Medicine and Langone Medical Center. Do not disclose or use except as authorized in writing by the study sponsor

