4.5 Duration of Study Participation

While the study will be open for 3 years after beginning enrollment, the actual length of a study subject's participation is four weeks.

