4.7 Participant Withdrawal or Termination

Participants are free to withdraw from participation in the study at any time upon request. An investigator may terminate participation in the study if:

- Any clinical adverse event (AE), laboratory abnormality, or other medical condition or situation occurs such that continued participation in the study would not be in the best interest of the participant
- The participant meets an exclusion criterion (either newly developed or not previously recognized) that precludes further study participation

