6.1 General Approach

Intention-to treat. The primary analysis will follow the intention-to-treat (ITT) principle in order to evaluate the true outcome of the intervention as experienced by the patient who is blinded to the intervention.

Missing Data. It is anticipated that the data for some subjects will be incomplete for various reasons: missing daily-diary entries, refusal to answer a sensitive question on a questionnaire, onset of illness, loss-to-follow-up, etc. All occurrences of incomplete data will be investigated to carefully document the reasons for the missing data. If the primary outcome (amount of opioid used between 24 and 72 hours after surgery) cannot be ascertained with a reasonable degree of certainty, the patient will be excluded from the study.

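### The adverse-event window in 7.3 runs from the last day of participation and not from the block, so new non-serious events are recorded for a shorter time after an early exit

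*Combined protocol and SAP*

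**What the plan says.** The Protocol Summary gives the duration of administration as "Once during surgery". Section 7.3 starts AE recording at consent and continues it "until 7 (for non-serious AEs) or 30 days (for SAEs) after the last day of study participation".

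The end of participation is stated in two ways. Section 4.5 and the Summary put it at four weeks ("participation is four weeks"). In section 3.1, after discharge, staff "follow up with the patient on POD 7, POD 14 and POD 30". For a patient who leaves early, no section says which day counts as the last one.

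Section 4.7 lets patients withdraw at any time. It also lets an investigator end participation if "Any clinical adverse event (AE), laboratory abnormality, or other medical condition or situation occurs" and staying on would not be in the patient's best interest. Section 6.1 adds that if the primary outcome cannot be ascertained, "the patient will be excluded from the study". It does not say whether AE recording stops at that point.

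Section 7.3 contains further duties that bear on early exits. AEs on study are documented whatever their cause, and open AEs are followed until they resolve, the patient is lost, or the event is otherwise explained. The investigator must also notify the sponsor of "any death or adverse event occurring at any time after a subject has discontinued or terminated study participation" if it may reasonably be related to the study.

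Section 6.2 lists AEs, with nausea and constipation among the examples, as a secondary endpoint. It gives no time window or denominator for comparing them.

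**The concern.** All patients are exposed once, at a known time, so the natural clock for safety starts at the block. The clock in 7.3 is instead set by when the patient leaves. Because an AE can be the reason for leaving, the outcome being measured can shorten its own observation period.

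This matters for a between-arm comparison of AEs. With no common window in 6.2, a patient who left on POD 1 and a patient followed to POD 30 would enter the comparison as if they had been observed equally.

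The other provisions of 7.3 do not fully close the gap:

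- Following open events does not detect new ones.
- The duty to notify after exit applies only to events thought to be related, whereas 7.2.2 says that relationship should not decide what is reported. The duty is owed to the sponsor, and nothing says that the event enters the study's AE data.
- The instruction to report later events is given at the last scheduled visit, which a patient who leaves early may not reach.
- AE inquiry happens at study visits, and no visit or call is described after exit.

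**Working it through.** The plan states no AE rate, exit count or safety denominator, so there is no figure of its own to reproduce. The check is date arithmetic, followed by a scenario for size.

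**Inputs.** Block on day 0. Recording continues for 7 days (non-serious) or 30 days (serious) after the last day of participation (7.3). A completer leaves on day 28 (4.5) or POD 30 (3.1). Enrolment is 184, with 146 evaluable (4.6).

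**Step 1: completers.** End of recording = exit day + 7 or + 30.

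- Non-serious: 28 + 7 = 35, or 30 + 7 = 37.
- Serious: 28 + 30 = 58, or 30 + 30 = 60.

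**Step 2: early exits, by the same formula.**

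| Exit day | Non-serious recording ends | Days short of day 28 / POD 30 | Serious recording ends |
|---|---|---|---|
| 0 | 7 | 21 / 23 | 30 |
| 1 | 8 | 20 / 22 | 31 |
| 3 | 10 | 18 / 20 | 33 |
| 7 | 14 | 14 / 16 | 37 |
| 14 | 21 | 7 / 9 | 44 |

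For a POD 1 exit the formal difference from a completer is 35 − 8 = 27 or 37 − 8 = 29 days. The days after POD 30 have no scheduled contact behind them even for completers, so the more meaningful shortfall is the 20 to 22 days to the end of scheduled follow-up. The serious window reaches POD 30 in every row, including exit on day 0.

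**Step 3: share of recording days lost, under assumed exits.** The documents give no number of early exits. The only related figure is 184 − 146 = 38 patients (38/184 = 20.7%) allowed as not evaluable. That is not a count of early exits: 6.1 expects incomplete data from missed diary entries and refused questions as well. It serves only as an assumed ceiling.

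With k exits on day 3 and completers leaving at POD 30, each exit loses 30 − 3 = 27 days from either window. Loss = k × 27 / (184 × full window).

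- Non-serious, k = 5: 135 / (184 × 37) = 135 / 6,808 = 2.0%.
- Non-serious, k = 38: 1,026 / 6,808 = 15.1%.
- Serious, k = 5: 135 / (184 × 60) = 135 / 11,040 = 1.2%.
- Serious, k = 38: 1,026 / 11,040 = 9.3%.

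These are lost observation days, not missed events.

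**Step 4: what remains covered after exit.**

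| Event | Covered by 7.3? |
|---|---|
| The AE that led to exit | Yes: recorded whatever its cause, and followed while unresolved |
| New event, reasonably related, any later time | Sponsor is notified; entry into the AE data not stated |
| New serious AE within 30 days of exit | Yes |
| New non-serious AE within 7 days of exit | Yes |
| New non-serious AE later than that, unrelated or not recognised as related | No |
| New serious AE more than 30 days after exit, judged unrelated | No, but this falls after scheduled follow-up |

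**The case against.** The strongest reply is that 7.3 already protects the patients who matter most. For someone terminated because of an AE, that event is recorded and actively followed with no 7- or 30-day cap. A reader might infer that such patients have the shortest safety follow-up overall. For events still open at exit, that is wrong.

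A reader might also infer that AEs in these patients are undercounted. The documents do not show this. They give no AE rates or timing, and later events judged related must be notified without time limit. Nor do they support a gap in serious AEs during scheduled follow-up. Respiratory depression or reintubation would often meet the seriousness criteria of 7.1 and so fall under the longer window. Section 2 describes the agent as acting for up to 72 hours, so even a POD 8 closure lies beyond the stated period of action.

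Bias in favour of one arm is a further tempting inference. Nothing in the documents suggests that exits differ by arm, and with a single administration there is no continuing study drug to stop for intolerance.

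These replies stand, and they confine the point to new non-serious AEs. They do not remove it: the window length still depends on the exit day, the last day is undefined for early exits, and no common comparison window is stated.

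**Conclusion.** The point holds in a limited form. Recording of new non-serious AEs can end on POD 7 to 21 for exits on days 0 to 14, against POD 35 to 37 for completers, and an AE can itself bring that exit about. The possible loss is mainly new non-serious AEs that start more than 7 days after exit and are unrelated or not recognised as related. Some related events may also be missing from the AE data if notification to the sponsor does not lead to an entry there.

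The dates rest on reading the last day of participation as the day of exit, which is the natural reading but is not defined. The scenario range of 2.0% to 15.1% of non-serious recording days rests on assumed exits on day 3, and its upper end needs all 38 non-evaluable patients to have left that early. The number of events missed, and the size or direction of any difference between arms, cannot be derived from the documents. The effect is probably small, but the rule is easily corrected.

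**What to change.** In 7.3, define the AE and SAE recording window from the block, for every patient who received one, running at least to the POD 30 contact whether or not participation ended early. There is no need to extend it beyond the last scheduled contact.

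Keep the AE inquiries at POD 7, 14 and 30 for patients whose participation has ended, unless they withdraw consent to contact. In that case use the medical record where consent allows. Say explicitly that these calls include the AE question: 7.3 places it at study visits, and 3.1 lists only pain, opioid use and function for the calls.

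In 6.2, state that AEs are compared between arms over this common window. Reconcile the four-week participation in the Summary and 4.5 with the POD 30 contact in 3.1.

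The cost is a wording amendment, a few more AE calls or chart checks by staff who already make the follow-up calls, and possibly a line in the consent form. The consent pages were not available for review, so that line may already exist. Patients who withdraw consent to any further data collection will still have a shorter window.
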